**SAMPLE AND DATA COLLECTION.** All participants will collect fecal samples at Days 0, 28, 56, and the day when they recover from COVID-19-like illness (if before Day 56). Participants are considered having recovered from COVID-19-like illness when they fulfil the CDC guidelines for discontinuing home isolation for persons with COVID-19 who have symptoms (updated July 20, 2020): at least 10 days have passed since symptom onset, at least 24 h have passed since resolution of fever without the use of fever-reducing medications, and other symptoms have improved. Participants will be provided with supplies and instructions (Appendices 8.1, 8.2 and 16) to collect fecal samples at home using a collection kit developed by

describe the fecal sample on a data collection form based on the Bristol Stool Scale (Appendix 12) [17] and mail the samples and the form to the research team in a prepaid shipping box by following the written instructions in Appendix 18. For participants who require hospitalization during the study, they will collect a fecal sample after they recover (on or before Day 56) and repeat sample collection on Days 28 and 56 as appropriate.

All participants will evaluate objective and subjective symptoms, adverse events and medication changes twice a day (in the morning around 8 am and 2 h after dinner around 8 pm using the last 12 h as the recall period) and record fasting blood glucose if participant has T2DM (after at least 8 h of overnight fasting) and consumption of NBT-NM108 (treatment group) or water (control group) once a day from Day 1 to Day 28 or until they recover from COVID-19-like illness (whichever is later) and then once a week until Day 56 (i.e. in the mornings of Days 35, 42, 49 and 56). Participants will also report symptoms, fasting blood glucose if participant has T2DM and medication changes on the day that they recover from COVID-19like illness (if before Day 56). For measurement of body temperature (oral), oxygen saturation level, pulse rate and respiratory rate and fasting blood glucose if participant has T2DM, participants will be provided with devices and instructions to take the measurements; for the remaining subjective symptoms, participants will be asked to evaluate the severity of each symptom using categorical options of "none", "mild", "moderate", and "severe" or the severity of the symptoms as directed. Participants will be asked to record these data and any adverse events in the participant booklet (Appendices 8.1 and 8.2) and report to the research team on Castor (Appendices 9-11). For participants who are hospitalized during the study, they will stop collecting data themselves during hospitalization but body temperature (oral), pulse rate, respiratory rate, oxygen saturation level, fasting blood glucose if participant has T2DM, respiratory support and other data related to the clinical progress of COVID-19-like illness will be extracted from their medical records at the hospital. If these patients are discharged on or before Day 56, they will collect data on objective and subjective symptoms and medication changes twice a day and fasting blood glucose if

Protocol Title: COVGUT20

participant has T2DM once a day after they are discharged until they recover from COVID-19-like illness and once a week thereafter until Day 56.

Medical history and regular medications will be extracted from the primary care medical records. If participants are hospitalized during the study, clinical data related to COVID-19-like illness will be extracted from the hospital medical records.

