## **B.** Data Points

- Gut microbiota composition: fecal samples will be collected at Days 0, 28, 56 and the day when participants recover from COVID-19-like illness (if before Day 56)
- Clinical progress of COVID-19-like illness: 1) objective and subjective symptoms data will be collected twice a day from Day 1 to Day 28 or until they recover from COVID-19-like illness (whichever is later) and once a week thereafter until Day 56 (i.e. in the mornings of Days 35, 42, 49 and 56); and 2) COVID-19-like illness severity will be assessed at Days 1, 14, 28 and 56 using the categorization from FDA [18] and the Ordinal Scale for Clinical Improvement from the World Health Organization [19]
- Proportion of participants who are "alive and not admitted to the hospital" at Days 1, 14, 28 and 56
- Proportion of participants who visit the emergency room at Days 1, 14, 28 and 56
- Outcome of COVID-19-like illness (hospitalization or death) at Days 1, 14, 28 and 56
- Glucose homeostasis if the participant has T2DM: fasting blood glucose will be measured in the mornings from Day 1 to Day 28 or until they recover from COVID-19-like illness (whichever is later) and weekly thereafter until Day 56

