## D. Endpoints

- 1. Primary outcome:
  - Gut microbiota composition
- 2. Secondary outcomes:
  - At Days 1, 14, 28 and 56:
  - a) Outcome of COVID-19-like illness (hospitalization or death)
  - b) Proportion of participants who are "alive and not admitted to the hospital"
  - c) Proportion of participants who visit the emergency room
  - d) Proportion of participants who have complete resolution of all objective symptoms, i.e. all vital signs are within the normal range for at least 48 h, including body temperature (oral) 36.5-37.5°C (97.7-99.5°F), pulse rate 60-100/min, respiratory rate 12-20/min and oxygen saturation level at 95-100%
  - e) Proportion of participants who have complete resolution of subjective symptoms, i.e. absence of all COVID-19-like symptoms listed by CDC (updated May 13, 2020) for at least 48 h, including the presence of chills or "feeling feverish", cough, shortness of breath or difficulty breathing, fatigue, muscle or body aches, headache, new loss of taste or smell, sore throat, congestion or runny nose, nausea or vomiting and diarrhea
  - f) Proportion of participants who have complete resolution of subjective symptoms except fatigue and cough, i.e. absence of all COVID-19-like symptoms listed by CDC (updated May 13, 2020) for at least 48 h, including the presence of chills or "feeling feverish", cough, shortness of breath or difficulty breathing, fatigue, muscle or body aches, headache, new loss of taste or smell, sore throat, congestion or runny nose, nausea or vomiting and diarrhea
  - g) Illness severity based on the categorization from FDA [18] and the Ordinal Scale for Clinical Improvement from the World Health Organization [19]
  - h) Body temperature (oral)
  - i) Oxygen saturation level
  - i) Pulse rate
  - k) Respiratory rate
  - I) Fasting blood glucose
  - Time to complete resolution of all objective symptoms
  - Time to complete resolution of all subjective symptoms
  - Time to complete resolution of all subjective symptoms except fatigue and cough

Protocol Title: COVGUT20

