- Timing and Frequency: Prospective participants will complete one online self-administered preliminary survey and attend one virtual eligibility screening interview. All enrolled participants will record objective and subjective symptoms, adverse events and medication changes twice a day (in the morning after at least 8 h of overnight fasting at around 8 am and 2 h after dinner at around 8 pm) and fasting blood glucose (if the participant has T2DM) and intervention compliance once a day from Day 1 to Day 28 or until they recover from COVID-19-like illness (whichever is later). After they recover, they will record these data once a week until Day 56 (i.e. the mornings of Days 35, 42, 49 and 56 as appropriate). Participants will also record these data on the day that they recover from COVID-19-like illness (if before Day 56). If participants are hospitalized during the study, they will discontinue all data collection by themselves during hospitalization but relevant clinical data will be retrieved from the hospital medical records. If participants are discharged on or before Day 56, they will record objective and subjective symptoms, adverse events and medication changes twice a day (in the morning after at least 8 h of overnight fasting around 8 am and 2 h after dinner around 8 pm) and fasting blood glucose (if the participant has T2DM) once a day until they recover from COVID-19-like illness and thereafter record these data once a week until Day 56.

Protocol Title: COVGUT20

- Procedures for Audio/Visual Recording: Not applicable

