To monitor COVID-19-like symptoms, participants will evaluate their symptoms and report to the research team on Castor twice a day from Day 1 to Day 28 or until they recover from COVID-19-like illness (whichever is later) and once a week thereafter until Day 56 (i.e. the mornings of Days 35, 42, 49 and 56 as appropriate). For those who are hospitalized during the study, after they are discharged they will also be asked to evaluate their symptoms and report to the research team on Castor twice a day until they recover from COVID-19-like illness and once a week thereafter until Day 56. The study team will review the symptom diary within 24 h of each entry and follow up with the participants if the symptoms require medical attention. The study team will call all participants at least once a week to monitor their progress. Participants are also instructed to call 911 if they notice any of the following red flags: respiratory rate  $\geq$  30/min, pulse rate  $\geq$  125/min, oxygen saturation level  $\leq$  93%, severe shortness of breath at rest (inability to talk in full sentences), difficulty breathing, persistent pain/pressure in chest, cold/clammy/pale/mottled skin, new confusion or inability to wake up, blue lips or face, little or no urine output or hemoptysis. Participants with T2DM will be instructed to call the physician who normally manages their diabetes if their fasting blood glucose is < 60 mg/dL or > 300 mg/dL.

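### The post-discharge diary rule drops the Day 28 minimum, so 48 h resolution and time to resolution are measured more coarsely in discharged participants who recover before Day 28

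*Protocol*

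**What the plan says.** **General rule.** Protocol section 1.3 A (Sample and Data Collection) opens with all participants. It has them report symptoms twice daily "from Day 1 to Day 28 or until they recover from COVID-19-like illness (whichever is later) and then once a week until Day 56", the weekly days being "i.e. in the mornings of Days 35, 42, 49 and 56". Section 1.3 B says that "objective and subjective symptoms data will be collected twice a day from Day 1 to Day 28", or until recovery if that is later, with no exception for admission.

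**Post-discharge rule.** The same part of 1.3 A then says that participants discharged on or before Day 56 keep the diary "after they are discharged until they recover from COVID-19-like illness and once a week thereafter until Day 56". Section 1.9 A (Timing and Frequency) ends its version with "once a day until they recover from COVID-19-like illness and thereafter record these data once a week until Day 56". Section 4.7 E has them "report to the research team on Castor twice a day until they recover from COVID-19-like illness and once a week thereafter until Day 56". None of the three carries the Day 28 minimum, and none says on which days a weekly entry falls if recovery comes before Day 28.

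**Recovery and endpoints.** Recovery (1.3 A) requires at least 10 days since onset, at least 24 h free of fever without fever-reducing medication, and improvement in other symptoms. Section 1.3 D lists its resolution proportions "At Days 1, 14, 28 and 56". Items d to f require at least 48 h of normal vital signs or of absent symptoms. Three time-to-resolution endpoints follow.

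**The concern.** The protocol gives two schedules for the same people. Under the post-discharge version, the switch to weekly entries is set by recovery, which can be reached while symptoms persist. A discharged participant may meet the recovery definition at or soon after discharge and so have little or no twice-daily phase at home. If complete resolution comes after recovery, it falls in the stretch that is now sampled weekly.

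This matters because the sampling density would depend on hospitalization, which is itself a secondary outcome. If the arms differ in admissions, they also differ in how well resolution is ascertained. The SAP (Clinical Data Analysis) plans logistic regression at each time point, and Gray's test and Fine-Gray regression for time to resolution. It makes no provision for resolution times known only to within a week. Multiple imputation appears only as a sensitivity analysis.

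**Working it through.** The documents state no figure that depends on this schedule, so there is nothing to reproduce. The check counts diary entries.

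**Inputs.** General and post-discharge rules: Protocol 1.3 A, 1.3 B, 1.9 A and 4.7 E. Named weekly days 35, 42, 49 and 56: 1.3 A. Recall of 12 h per twice-daily entry: 1.3 A. The 48 h criterion: 1.3 D, items d to f. Recovery day R after discharge is not given and is varied.

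**Entries after recovery, up to and including Day 28.** Under the general rule the count is 2 × (28 − R). The weekly rule can be read in three ways:
- (i) the named days extended backwards on their 7-day grid (7, 14, 21, 28);
- (ii) every 7 days counted from R;
- (iii) only the named days, the first of which is Day 35.

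| R | General rule | (i) 7-day grid | (ii) from recovery | (iii) named days only |
|---|---|---|---|---|
| 10 | 2 × 18 = 36 | 3 (Days 14, 21, 28) | 2 (Days 17, 24) | 0 |
| 14 | 2 × 14 = 28 | 2 | 2 | 0 |
| 21 | 2 × 7 = 14 | 1 | 1 | 0 |
| 24 | 2 × 4 = 8 | 1 | 0 | 0 |
| 27 | 2 × 1 = 2 | 1 | 0 | 0 |

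**Is there an entry on the endpoint day?** Under (i), Day 28 always has one entry, and so does Day 14 when R is earlier. Under (ii), for R from 5 to 27 (23 days), Day 28 has an entry only for R = 7, 14 or 21, so it is missed for 20 of 23. Day 14 is missed for R = 5, 6, 8, 9, 10, 11, 12 and 13, that is 8 of 23. For R of 14 or later, Day 14 does not fall in the weekly phase.

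**Can one entry establish 48 h?** No separate recall period is given for weekly entries, so I assume the stated 12 h carries over. One entry then covers 12/48 = 25% of the required window and 12/168 = 7.1% of a week. Even where an entry falls on Day 28, it cannot confirm items d to f. It can supply a same-day temperature, oxygen saturation, pulse, respiratory rate or glucose value.

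**Who is affected?** Day 28 status is affected only if discharge and recovery both precede Day 28. Day 14 status is affected only if admission, discharge and recovery all precede Day 14. Time to resolution is affected only when resolution comes after recovery. No admission rate is given; an assumed 2% to 20% of 100 participants gives 2 to 20 admissions, and only the subset who recover before Day 28 is touched.

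**The case against.** A reader might infer that the Day 14 and Day 28 endpoints go mostly unmeasured in the sickest participants. The documents do not support that. Vital signs and clinical progress during a stay are taken from hospital records (1.3 A). Hospitalization and death come from medical records (1.9 B). Severity is scheduled separately at Days 1, 14, 28 and 56 (1.3 B), and stool collection continues after discharge (1.8 A), so the primary outcome does not depend on the diary. Anyone discharged but not yet recovered stays on twice-daily entries, so those ill longest are the least affected. Without an admission rate, length of stay or recovery day, no statement about most participants can be derived.

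The named weekly days are all multiples of 7, so reading (i) is natural, and it leaves an entry on both Day 14 and Day 28. Reading (iii), with nothing recorded until Day 35, sits badly with an instruction to record weekly after recovery. The count of 20 of 23 belongs to reading (ii) alone, an anchor that no section states.

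All of this stands and limits the point. It does not remove it: under every reading a lone entry falls short of 48 h, and the reader has to guess which reading applies. The weekly call in 4.7 E is for monitoring progress and is not described as recording vital signs. Hospital records of the stay end at discharge.

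A reader might also infer that product intake up to Day 28 is being lost, because the post-discharge lists omit it. Section 1.3 A (Interventions) stops all study procedures during hospitalization and does not say whether intervention restarts afterwards. If it does not restart, the omission is coherent. The documents support only a call for clarity.

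**Conclusion.** The point holds in limited form. The post-discharge sentences in 1.3 A, 1.9 A and 4.7 E conflict with the general rule in 1.3 A and with 1.3 B. Followed literally, they leave the 48 h resolution proportions (chiefly at Day 28, and at Day 14 only when recovery precedes it) and the time-to-resolution endpoints on a coarser footing for participants discharged and recovered before Day 28. For those individuals the loss is large: 0 to 3 entries instead of 36 for recovery on Day 10. For the trial it is probably small, since it concerns secondary endpoints in an unknown but likely small number of people. Any bias between arms would require admissions, or the timing of recovery after discharge, to differ by arm.

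The Day 56 criterion is no worse for discharged participants: everyone who has recovered is on weekly entries by then. The conclusion rests on the 12 h recall applying to weekly entries and on the home diary being the only described source of post-discharge vital signs and symptoms.

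**What to change.** In sections 1.3 A, 1.9 A and 4.7 E, replace the post-discharge schedule with the one the protocol already uses: twice daily to the later of Day 28 and recovery, then Days 35, 42, 49 and 56. This agrees with 1.3 B, restores 2 × (28 − R) entries between recovery and Day 28, and removes the question of how the weekly entries are anchored before Day 35. The participant booklet needs the same edit. The cost is one sentence in three places and a few more diary entries for a few participants, with no new form or visit.

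Separately, sections 1.3 A (Interventions and Sample and Data Collection) and 1.9 A should be reconciled on whether intervention continues after discharge, and the post-discharge item lists aligned with the answer. At present both lists omit intake, and adverse events appear in the 1.9 A list but not in the 1.3 A list. This is a request for consistency and does not presume that the product resumes.

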## **B.** Data Points

- Gut microbiota composition: fecal samples will be collected at Days 0, 28, 56 and the day when participants recover from COVID-19-like illness (if before Day 56)
- Clinical progress of COVID-19-like illness: 1) objective and subjective symptoms data will be collected twice a day from Day 1 to Day 28 or until they recover from COVID-19-like illness (whichever is later) and once a week thereafter until Day 56 (i.e. in the mornings of Days 35, 42, 49 and 56); and 2) COVID-19-like illness severity will be assessed at Days 1, 14, 28 and 56 using the categorization from FDA [18] and the Ordinal Scale for Clinical Improvement from the World Health Organization [19]
- Proportion of participants who are "alive and not admitted to the hospital" at Days 1, 14, 28 and 56
- Proportion of participants who visit the emergency room at Days 1, 14, 28 and 56
- Outcome of COVID-19-like illness (hospitalization or death) at Days 1, 14, 28 and 56
- Glucose homeostasis if the participant has T2DM: fasting blood glucose will be measured in the mornings from Day 1 to Day 28 or until they recover from COVID-19-like illness (whichever is later) and weekly thereafter until Day 56

## C. Study Duration

It will take each participant 56 days to complete the study. The overall duration of the study is 10 months.

## D. Endpoints

- 1. Primary outcome:
  - Gut microbiota composition
- 2. Secondary outcomes:
  - At Days 1, 14, 28 and 56:
  - a) Outcome of COVID-19-like illness (hospitalization or death)
  - b) Proportion of participants who are "alive and not admitted to the hospital"
  - c) Proportion of participants who visit the emergency room
  - d) Proportion of participants who have complete resolution of all objective symptoms, i.e. all vital signs are within the normal range for at least 48 h, including body temperature (oral) 36.5-37.5°C (97.7-99.5°F), pulse rate 60-100/min, respiratory rate 12-20/min and oxygen saturation level at 95-100%
  - e) Proportion of participants who have complete resolution of subjective symptoms, i.e. absence of all COVID-19-like symptoms listed by CDC (updated May 13, 2020) for at least 48 h, including the presence of chills or "feeling feverish", cough, shortness of breath or difficulty breathing, fatigue, muscle or body aches, headache, new loss of taste or smell, sore throat, congestion or runny nose, nausea or vomiting and diarrhea
  - f) Proportion of participants who have complete resolution of subjective symptoms except fatigue and cough, i.e. absence of all COVID-19-like symptoms listed by CDC (updated May 13, 2020) for at least 48 h, including the presence of chills or "feeling feverish", cough, shortness of breath or difficulty breathing, fatigue, muscle or body aches, headache, new loss of taste or smell, sore throat, congestion or runny nose, nausea or vomiting and diarrhea
  - g) Illness severity based on the categorization from FDA [18] and the Ordinal Scale for Clinical Improvement from the World Health Organization [19]
  - h) Body temperature (oral)
  - i) Oxygen saturation level
  - i) Pulse rate
  - k) Respiratory rate
  - I) Fasting blood glucose
  - Time to complete resolution of all objective symptoms
  - Time to complete resolution of all subjective symptoms
  - Time to complete resolution of all subjective symptoms except fatigue and cough

Protocol Title: COVGUT20

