# C. Subject Screening

# Inclusion Criteria

- Aged between 18 to 79 (inclusive)
- Have mild to moderate COVID-19-like symptoms based on the symptom list from CDC (updated May 13, 2020) and the severity categorization from FDA [18]:
  - a) Mild COVID-19

- Fever or chills, cough, shortness of breath or difficulty breathing, fatigue, muscle or body aches, headache, new loss of taste or smell, sore throat, congestion or runny nose, nausea or vomiting, and diarrhea
- · No clinical signs indicative of moderate, severe, or critical illness severity
- b) Moderate COVID-19
  - Symptoms of moderate illness with COVID-19 could include any symptom of mild illness or shortness of breath with exertion
  - Clinical signs suggestive of moderate illness with COVID-19, such as respiratory rate ≥ 20 breaths/min, oxygen saturation level > 93% on room air at sea level, heart rate ≥ 90 beats/min
  - No clinical signs indicative of severe or critical illness severity.
- Directed to home isolation by study physician

\_

- Practice acceptable contraception, i.e., continue with current methods if participants are already
  practicing contraception, otherwise parti cipants must agree to practicing contraception with a
  barrier method (male or female condom) or abstinence, from Day 1 to Day 35 or 7 days after the
  last dose of NBT-NM108 if they do not complete the 28-day intervention.
- Have access to a smartphone, tablet, computer, or other qualifying internet-enabled device and daily internet access
- Understand and be able to follow written and oral instructions in English
- Provide informed consent

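### The objective-resolution endpoint counts low temperature, pulse and respiratory rate against recovery, although the protocol's COVID-19 signs for these measures are high values only

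*Protocol*

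**What the plan says.** Protocol section 1.3 D, secondary outcome (d), is the proportion with complete resolution of all objective symptoms at Days 1, 14, 28 and 56. Resolution means that "all vital signs are within the normal range for at least 48 h", with the ranges "body temperature (oral) 36.5-37.5°C (97.7-99.5°F), pulse rate 60-100/min, respiratory rate 12-20/min and oxygen saturation level at 95-100"%. Time to complete resolution of all objective symptoms is a further secondary outcome.

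Vital signs are recorded "twice a day (in the morning around 8 am and 2 h after dinner around 8 pm using the last 12 h as the recall" window (section 1.3 A), from Day 1 to Day 28 or recovery, whichever is later, and weekly after that.

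The protocol describes COVID-19 illness in these measures in three other places:

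- **Section 4.1 C, Inclusion Criteria.** The mild list opens "Fever or chills, cough, shortness of breath or difficulty breathing, fatigue, muscle or body aches, headache". The signs suggestive of moderate illness are "respiratory rate ≥ 20 breaths/min, oxygen saturation level > 93% on room air at sea level, heart rate ≥ 90 beats/min".
- **Section 1.3 A, recovery.** The temperature condition is that "at least 24 h have passed since resolution of fever without the use of fever-reducing medications". There is no lower limit.
- **Section 4.7 E, red flags.** Respiratory rate of 30/min or more, pulse of 125/min or more, and oxygen saturation of 93% or below.

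The SAP (Clinical Data Analysis) and protocol section 6.1 compare the proportions by a separate logistic regression at each time point and the times by competing-risks survival analysis. Neither redefines the endpoint or makes an exception for a participant's usual values.

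**The concern.** The endpoint is named resolution of symptoms, yet three of its limits (36.5°C, 60/min and 12/min) exclude values that the protocol never treats as a symptom. A participant who never had fever but reads 36.3°C one morning, or whose resting pulse is 56/min, has an unresolved objective symptom under the rule. Each such reading breaks the 48 h window. The participant is counted as unresolved at that time point, and in the time-to-event analysis as resolving later or not within follow-up.

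What is at stake is the ability of these two analyses to detect a difference. If people who are well are recorded as unresolved for reasons unconnected with COVID-19, a real effect on fever, fast pulse, fast breathing or low saturation is harder to see.

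**Working it through.** **1. Each lower limit against the protocol's illness signs.**

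| Measure | Lower limit in endpoint (d) | Signs in 1.3 A, 4.1 C and 4.7 E | Low value a COVID-19 sign? |
|---|---|---|---|
| Oral temperature | 36.5°C | fever or chills; resolution of fever | No |
| Pulse | 60/min | ≥ 90/min; ≥ 125/min | No |
| Respiratory rate | 12/min | ≥ 20/min; ≥ 30/min | No |
| Oxygen saturation | 95% | red flag ≤ 93% | Yes |

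The nearest thing to a cold sign is cold or clammy skin among the red flags, which is a skin finding and not an oral temperature. The saturation limit does face the direction of illness and is not part of this point.

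**2. Is 36.5°C a conversion slip?** No. 36.5 × 9/5 + 32 = 97.7°F and 37.5 × 9/5 + 32 = 99.5°F, as printed.

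**3. Readings per window.** With readings about 12 h apart, 48 h holds 4 to 5 of them, at least 2 in the morning. The protocol gives no count. Five consecutive readings span exactly 48 h.

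**4. Why a small per-reading chance matters.** Let *f* be the chance, assumed, that one reading in a well person falls below a lower limit. With *k* independent readings the share counted as resolved is (1 − *f*)^*k*. If readings were fully correlated within a person it would be 1 − *f*.

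| *f* | *k* = 4 | *k* = 5 | Fully correlated |
|---|---|---|---|
| 0.02 | 92% | 90% | 98% |
| 0.05 | 82% | 77% | 95% |
| 0.10 | 66% | 59% | 90% |
| 0.20 | 41% | 33% | 80% |

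**5. Illustration for temperature only.** The documents give no temperature distribution, so all inputs here are assumptions: afebrile mean *m* from 36.4 to 37.0°C, between-person SD *s_b* and within-person SD *s_w* each 0.20 or 0.25°C, readings rounded to 0.1°C, and five consecutive readings. For a person with own mean *b*, the chance that one reading is in range is Φ((37.55 − *b*)/*s_w*) − Φ((36.45 − *b*)/*s_w*). This is raised to the fifth power and averaged over *b* ~ N(*m*, *s_b*²). The upper-limit-only version drops the second term. The last column comes from simulating 56 twice-daily readings.

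| Mean | Meets rule, 48 h to Day 14 | Upper limit only | No qualifying 48 h window by Day 28 |
|---|---|---|---|
| 36.4°C | 9-16% | about 100% | 54-56% |
| 36.6°C | 29-38% | 98-100% | 21-26% |
| 36.8°C | 52-67% | 94-98% | 4-8% |
| 37.0°C | 62-81% | 81-91% | 1-3% |

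If four readings are enough to span 48 h, the last column at the first three means falls to about 44-47%, 14-20% and 2-5%. Pulse and respiratory rate are not modelled.

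**6. What dilution would do to the logistic comparison.** Assume true resolution rates of 60% v 85% and 50 per arm (section 1.5), with two-sided alpha 0.05. The pooled proportion is 0.725. The null standard error is √(2 × 0.725 × 0.275/50) = 0.0893, and the alternative one is √((0.60 × 0.40 + 0.85 × 0.15)/50) = 0.0857. Power is Φ((0.25 − 1.96 × 0.0893)/0.0857) = 0.81. If only a share *s* of truly resolved participants is counted as resolved, equally in both arms, the rates become 0.60*s* and 0.85*s*. Power is then 0.53 (*s* = 0.8), 0.33 (*s* = 0.6) and 0.19 (*s* = 0.4). The documents state no power for this endpoint, so these figures show direction and scale only.

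**The case against.** The strongest reply is that the effect is unquantified and confined to one composite. Much of that stands.

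- **The size depends on an input the documents do not give.** Shifting the assumed mean by 0.4°C moves the Day 14 share from about 9-16% to 52-67%. At 37.0°C, the midpoint of the protocol's range, the upper limit alone already brings it down to 81-91%, so only about half of the shortfall comes from the lower limit. The percentages are illustrations.
- **The Day 14 figures take the 48 h to end at that day.** The protocol does not say whether the window must end then or may have been met earlier. Under the second reading fewer people are misclassified.
- **The information is partly held elsewhere.** Temperature, saturation, pulse and respiratory rate are separate secondary outcomes with longitudinal models, and time to recovery uses a definition with no lower temperature limit. The primary outcome and the sample size concern gut microbiota.

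Three stronger readings are tempting, and the documents support none of them. A reader might infer that the endpoint largely measures constitutional temperature and pulse. That fits only the cooler assumed means, and nothing here quantifies pulse. A reader might infer that recovered participants will never be counted as resolved. Readings continue twice daily to at least Day 28, and under most of the assumed means most well people have a qualifying window by then, so many would be late and not lost. A reader might also infer bias, or assert that NBT-NM108 cannot affect usual temperature or pulse. The documents are silent on the second, and misclassification unrelated to arm costs sensitivity without showing bias.

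That the limits are simply a normal range does not answer the point. The endpoint claims to measure resolution of symptoms, and a value the protocol never treats as a symptom has nothing to resolve.

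**Conclusion.** The definitional point holds on the text alone. Endpoint (d) and its time-to-event version require lower limits on temperature, pulse and respiratory rate that correspond to no COVID-19 sign in the protocol, and neither document exempts usual values. The consequence is misclassification unrelated to COVID-19 and reduced sensitivity in two secondary analyses. Its size is unknown. It could be small if participants run warm, or substantial if they run cool, and it rests on the assumed mean, the SDs and the number of readings taken to span 48 h. The correction is worth making before analysis, but the point does not threaten the trial's main conclusion.

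**What to change.** For endpoint (d) and time to complete resolution of all objective symptoms only, state that a vital sign counts as unresolved when it is out of range in the direction of illness. The lower limits on temperature, pulse and respiratory rate then no longer count against resolution. Keep the plan's other limits for now, and carry the same wording into the SAP, which at present does not define the endpoint.

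The sponsor should also reconcile the limits that remain with the illness signs in sections 1.3 A, 4.1 C and 4.7 E. The endpoint accepts a pulse up to 100/min and a respiratory rate up to 20/min as normal, while the inclusion criteria list a heart rate of 90/min or more and a respiratory rate of 20/min or more as suggestive of moderate illness. A participant at 95/min and 20/min is resolved under one passage and shows moderate signs under the other. Which values are right is for the sponsor to settle.

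The cost is one line in the endpoint definition and its counterpart in the SAP. The readings are already collected, and care and alert rules do not change.
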